 - Any Grade ≥ 3 non-hematologic toxicity except:
 - Nausea, vomiting, and/or diarrhea of Grade 3 severity that resolves within 7 consecutive days with optimal prophylaxis and/or treatment;
 - Grade 3 fatigue that resolves to Grade ≤ 2 within 7 consecutive days;
 - Grade ≥ 3 alkaline phosphatase that is related to underlying malignancy (eg, bone metastasis).
 - Grade ≥ 3 asymptomatic or mildly symptomatic rash will not be considered a DLT if the event can be adequately managed with supportive care, the event resolves to become asymptomatic and/or Grade ≤ 2 within 7 days, or the event continues for longer than 7 days in a patient who has not received appropriate supportive therapy.
 - Grade ≥ 3 elevation of serum creatine phosphokinase (CPK) level will not be considered a DLT if the event is asymptomatic (i.e., not accompanied by signs, symptoms, or other laboratory abnormalities associated with rhabdomyolysis or myocardial injury) and is deemed by the investigator to be clinically insignificant.
 - Grade 3 arthralgia will not be considered a DLT if the event can be adequately managed with supportive care or the event resolves to Grade ≤ 2 within 7 days.
 - Grade 3 fever (in the absence of any clinically significant source of fever) will not be considered a DLT if the event resolves to Grade ≤ 2 within 7 days or the event continues for longer than 7 days in a patient who has not received appropriate supportive care.

- Grade 3 laboratory abnormality will not be considered a DLT if the event is asymptomatic and is deemed by the investigator to be clinically insignificant.
- Grade 3 autoimmune thyroiditis or other endocrine abnormality will not be considered a DLT if the event can be managed by endocrine therapy that would not necessitate initiation of systemic corticosteroids.
- Grade ≥ 3 total bilirubin that is not attributed to disease progression
- Grade ≥ 3 AST or ALT, but not isolated elevation in ALT (non-specific) in subjects without metastatic disease in the liver
- AST or ALT $\geq 10X$ ULN in subjects with liver metastasis
- QTc interval ≥ 501 ms confirmed by a repeat ECG
- Grade ≥ 3 Creatine Kinase with symptoms of myalgia
- Grade ≥ 2 retinal events lasting greater than 14 days or Grade ≥ 3 retinal events that are confirmed by ophthalmologic examination
- Grade ≥ 3 rash that persists despite optimal treatment, and that does not resolve to Grade ≤ 2 within 7 days.

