Defined as having a positive hepatitis B surface antigen (HBsAg) test at screening. Patients with a past or resolved HBV infection, defined as having a negative HBsAg test and a positive total hepatitis B core antibody test at screening, are eligible for the study.

15. Active hepatitis C virus (HCV) infection

Defined as positive HCV antibody test followed by a positive HCV RNA test at screening. The HCV RNA test will be performed only for patients who have a positive HCV antibody test.

16. Known clinically significant liver disease, including alcoholic hepatitis, cirrhosis, fatty liver disease, and inherited liver disease

17. Active tuberculosis

18. Severe infection

Patients may not have had a severe infection within 4 weeks prior to initiation of study treatment. This includes, but is not limited to, hospitalization for complications of infection, bacteremia, or severe pneumonia. However, patients who were admitted for biliary tract infection due to bile duct obstruction at time of diagnosis must have a functioning biliary stent (as evidenced by declining total bilirubin and $\leq 2X$ ULN) and resolved infection (defined by normalization of elevated white blood cell count, absence of signs of infection) and completion of an antibiotic course (at least a seven-day course) prior to initiation of therapy.

Columbia University Irving Medical Center
Herbert Irving Comprehensive Cancer Center
AAAS4165_Version Date: 07/07/2021

19. Recent antibiotic treatment

Patients may not have been treated with therapeutic oral or intravenous (IV) antibiotics within 2 weeks prior to initiation of study treatment, except for biliary tract infection due to bile duct obstruction from the pancreas mass. Patients receiving prophylactic antibiotics (e.g., to prevent a urinary tract infection or chronic obstructive pulmonary disease exacerbation) are eligible for the study.

20. Significant cardiovascular disease

Patient may not have significant cardiovascular disease (such as New York Heart Association Class II or greater cardiac disease, myocardial infarction, or cerebrovascular accident) within 12 months prior to initiation of study treatment, seizure disorder, uncontrolled hypertension, or unstable arrhythmia or unstable angina within 3 months prior to initiation of study treatment.

21. Left ventricular ejection fraction below institutional lower limit of normal or below 50%, whichever is lower

22. Baseline QTcF \geq 450 ms (males) or \geq 470 ms (females)

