7. TREATMENT AND/OR IMAGING PLAN

7.1 Investigational Agent Administration

Treatment will be on an outpatient basis. Reported AEs and potential risks for cobimetinib, hydroxychloroquine, and atezolizumab are described below (Section 8, Appendix 1). Appropriate dose modifications are described in Section 9. No investigational or commercial agents or therapies other than those described below may be administered to treat the patient's malignancy.

Patients will receive treatment as outlined in Table 4 below until unacceptable toxicity or loss of clinical benefit, as determined by the investigator after an integrated assessment of radiographic

Columbia University Irving Medical Center
Herbert Irving Comprehensive Cancer Center
AAAS4165_Version Date: 07/07/2021

and biochemical data, local biopsy results (if available), and clinical status (e.g., symptomatic deterioration such as pain secondary to disease).

Columbia University Irving Medical Center
Herbert Irving Comprehensive Cancer Center
AAAS4165_Version Date: 07/07/2021

Table 4. Treatment schedule

| Cycle | Cycle Length | Dose, Route and Regimen (drugs listed in order of administration) |
|--------------------|---------------------|--|
| Cycle 1 and beyond | 28 days | 
• Cobimetinib^a orally once daily (morning) on Days 1-21 of each 28-day• Hydroxychloroquine: 600mg orally twice daily on Days 1-28 of each 28-day cycle• Atezolizumab None or 840 mg IV on Days 1 and 15 of each cycle |

^aDose will be determined via dose levels

If one study drug is discontinued, the other study drug(s) can be continued if the patient is likely to derive clinical benefit, as determined by the investigator in consultation with the Principal Investigator.

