8.3.1 Cobimetinib-associated adverse events

For specific guidelines on how to respond to adverse events associated with cobimetinib, see Appendix 1.

The following adverse events are classified as identified risks associated with cobimetinib: serious retinopathy, left ventricular dysfunction, severe hemorrhage, rhabdomyolysis, and pneumonitis. The following adverse events are classified as potential risks for cobimetinib: severe hepatotoxicity (Grade ≥ 3), impaired female fertility, and teratogenicity and developmental toxicity. In addition, there is the possibility of drug-drug interactions in patients treated with cobimetinib. Clinical and safety data were reported that included monotherapy and combination

studies, of which key adverse events are summarized here, but for a complete review of the safety data please refer to the most current IB version.

Common (>10%) adverse events observed with Cobimetinib included bleeding, serious retinopathy, diarrhea, nausea, emesis, rash, pyrexia, chills, anemia, increased liver function enzymes, increased creatinine phosphokinase, and photosensitivity. Less common (1% - 10%) adverse events included decreased left ventricular ejection, risk of basal and squamous cell carcinoma, kertocanthoma, dehydration, hyponatremia, hypophosphatemia, hyperglycemia, and pneumonitis. Guidelines for treatment interruption or discontinuation in the case of adverse events are described in Appendix 1.

Cobimetinib should be permanently discontinued for:

- Grade 4 hemorrhage events attributed to cobimetinib
- Symptomatic or asymptomatic decrease of LVEF < 40% or $\geq 10\%$ absolute decrease from baseline after treatment break or recurrent symptomatic absolute decrease of LVEF < 10% (See Table 1 for details)
- Rhabdomyolysis or symptomatic CPK elevations not improving within 4 weeks of dose interruption
- Liver laboratory abnormalities not resolving to Grade ≤ 1 within 4 weeks of dose interruption or if Grade 4 liver laboratory abnormalities recur after initial improvement
- QTc increase meets values of both > 500 ms and > 60 ms change from pre-treatment values or 3rd occurrence of QTc > 500 ms during treatment and change from pre-treatment value remains ≤ 60 ms

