Hydroxychloroquine is a small water soluble compound (MW 433.95) that is dispensed in 200 mg tablets for oral administration. In healthy males, peak blood concentration was reached in 3.26 hours with a half life of 537 hours (22.4 days). The plasma peak concentration was reached in 3.74 hours with a half life of 2,963 hours (123.5 days). The long half-life can be attributed to extensive tissue uptake rather than through decreased excretion. In subjects taking the drug chronically for six months, renal clearance of the drug appeared similar.

Hydroxychloroquine is prescribed for Malaria, Rheumatoid Arthritis, and Systemic Lupus Erythematosus by an unknown mechanism.

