3. A post-study follow-up contact by phone by site staff will be conducted every 3 months during years 1 and 2, then every 6 months thereafter to obtain information on any new anti-cancer therapy received and survival status.
4. Initial diagnosis of adenocarcinoma and KRAS mutation status needs to be confirmed by a CLIA certified pathology.
5. A complete physical examination will be performed at screening. All subsequent physical examinations will be disease-specific on Cycle 1 days 1, 8, 15, 22; Cycle 2 and 3 days 1 and 15; day 1 and 15 on each subsequent cycle, and at the End-of-Study visit.
6. ECG will be performed after the patient has been in a supine position for at least 5 minutes. It will be performed at screening, cycle 1 day 15, day 1 of every subsequent cycle, and at the End-of-Study visit.
7. ECHO or MUGA scan should be performed at screening, day 1 of cycle 2, every 3 months (+ 1 week) thereafter and at the end of study visit.

Columbia University Irving Medical Center
Herbert Irving Comprehensive Cancer Center
AAAS4165_Version Date: 07/07/2021

8. A complete blood count with differential and comprehensive metabolic panel including glucose, calcium, albumin, total protein, sodium, potassium, CO2 (carbon dioxide, bicarbonate), chloride, BUN (blood urea nitrogen), creatinine, ALP (alkaline phosphatase), ALT (alanine amino transferase), AST (aspartate amino transferase) and bilirubin will be performed on Cycle 1 days 1, 8, 15, and 22; Cycle 2 and 3 days 1 and 15; on day 1 and 15 of each subsequent cycle, and at the End-of-Study visit.
9. An Ophthalmologic examination should be performed during the screening period, and on cycle 3 day 1 (+ 7 days), every 12 weeks (+ 7 days) thereafter, and at the End-of-Study visit if not performed within 6 weeks. The baseline exam should include: best corrected distance visual acuity (BCVA), an automated threshold visual field (VF) of the central 10 degrees (with retesting if an abnormality is noted), and spectral domain ocular coherence tomography (SD-OCT). Each subsequent examinations should include BCVA, VF and SD-OCT. In patients of Asian descent, it is recommended that visual field testing be performed in the central 24 degrees instead of the central 10 degrees.

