^a Resuming atezolizumab may be considered in patients who are deriving benefit and have fully recovered from the immune-related event. Patients can be re-challenged with atezolizumab only

Table A1.12. Guidelines for managing electrocardiogram QT corrected interval prolonged in response to *atezolizumab, cobimetinib, and/or hydroxychloroquine*.

| Event | Action |
|--|--|
| QTc > 500ms and change from pre-treatment value remains $\leq 60\text{ms}$ | |
| 1st Occurrence | Temporarily interrupt treatment until QTc decreases below 500 ms; reduce Cobimetinib by 1 dose level |
| 2nd Occurrence | Temporarily interrupt treatment until QTc decreases below 500 ms; reduce Hydroxychloroquine by 1 dose level |
| 3rd Occurrence grade 3 | Temporarily interrupt treatment until QTc decreases below 500 ms; reduce Cobimetinib and Hydroxychloroquine by 1 more dose level |
| Grade 4 Torsade de pointes; polymorphic ventricular tachycardia; signs/symptoms of serious arrhythmia | Permanently discontinue study drugs |
| QTc increase meets values of both $> 500\text{ ms}$ and $> 60\text{ ms}$ change from pre-treatment values | |
| 1st Occurrence | Discontinue drugs permanently |

Drugs should be interrupted for 3 ± 2 days and Electrocardiogram repeated until QTc below 500ms for four attempts. Subject should be referred to an electro cardiologist if QTc does not decrease below 500ms after study drug held for greater than 7 days (consecutively).

Table A1.13. Guidelines for managing rhabdomyolysis or CPK elevation in response to *atezolizumab, cobimetinib, and/or hydroxychloroquine*.

| Event | Action |
|---|---|
| Rhabdomyolysis or CPK elevation | |
| General guidance | 
 • Evaluate for cardiac cause (check ECG, serum cardiac troponin, and CPK-isoforms M and B fraction) and rhabdomyolysis (clinical examination; serum creatinine, potassium, calcium, phosphorus, uric acid, and albumin; and urine myoglobin). • Assess patient for any history of strenuous physical activity, blunt trauma, or recent IM injections. |
| Asymptomatic CPK elevation, Grade 1, 2, or 3 | 
 • Continue study drugs. • Recheck CPK at least once a week. |

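### Entry is screened on QTcF but the DLT, hold and discontinuation rules name no QT correction, and from Cycle 2 the scheduled on-treatment ECGs that inform the cobimetinib QTc rules nominally follow its off-week

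*Combined protocol and SAP*

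**What the plan says.** **Correction formula.** Exclusion criterion 22 in Section 5.2 is set on "Baseline QTcF": men are excluded at 450 ms or more and women at 470 ms or more. This is the only place where the protocol names a correction. Section 4.1.1.1 counts as a DLT a QTc of 501 or more "ms confirmed by a repeat ECG". Section 8.3.1 stops cobimetinib permanently if the "QTc increase meets values of both > 500 ms and > 60 ms change from pre-treatment values", or at a third QTc above 500 ms with a change of 60 ms or less. Table A1.12 uses the same 500 and 60 ms limits. None of these three rules names a correction, and 8.3.1 and Table A1.12 both use a change from the pre-treatment value.

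**ECG calendar.** Footnote 6 to Table 10 says of the ECG: "It will be performed at screening, cycle 1 day 15, day 1 of every subsequent cycle, and at the End-of-Study visit". In Table 4, cobimetinib is taken "orally once daily (morning) on Days 1-21 of each 28-day" cycle, whereas hydroxychloroquine is given at "600mg orally twice daily on Days 1-28 of each 28-day cycle". The first step in Table A1.12, for a QTc above 500 ms with a change of 60 ms or less, is: "Temporarily interrupt treatment until QTc decreases below 500 ms; reduce Cobimetinib by 1 dose level".

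**The concern.** Bazett and Fridericia values agree only at 60 bpm. If a site reads on-study ECGs with a formula other than the entry one, a threshold can be met or missed with no change in the patient, and a change from pre-treatment mixes two scales. The confirmatory ECG does not help if it is read with the same formula. A DLT carries weight here: the first one ends the cohort stage and starts the TITE-CRM, escalation immediately after a DLT is barred, and the trial has 18 patients. Under Section 8.1 the patient also leaves the study unless deriving benefit.

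The calendar raises a different question. Cobimetinib is the first drug reduced in Table A1.12 and has its own QTc stopping rule in 8.3.1. From Cycle 2, the scheduled ECGs that inform those actions are taken when cobimetinib has been off for a week.

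**Working it through.** The plan gives no figure on this point to reproduce.

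**1. Effect of the formula.** With RR in seconds, QTcF = QT/RR^(1/3) and Bazett QTcB = QT/RR^(1/2). Hence QTcB = QTcF × (HR/60)^(1/6). The inputs are the highest eligible whole-millisecond values, 469 (women) and 449 (men), with QTcF held unchanged. That a site reads Bazett is assumed.

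| Heart rate (bpm) | Factor | QTcB from 469 | QTcB from 449 |
|---|---|---|---|
| 80 | 1.0491 | 492.0 | 471.1 |
| 90 | 1.0699 | 501.8 | 480.4 |
| 100 | 1.0889 | 510.7 | 488.9 |
| 120 | 1.1225 | 526.4 | 504.0 |

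- Heart rate at which QTcB reaches 501 ms, 60 × (501/QTcF)^6: 89 bpm from 469, 116 bpm from 449, 150 bpm from 430.
- Heart rate at which the apparent rise passes 60 ms, 60 × ((QTcF + 60)/QTcF)^6: 124 bpm from 469, rising to 134 bpm from 420. At 90 and 100 bpm the gap from 469 is 32.8 and 41.7 ms, short of 60.
- In the other direction, QTcF 501 at 50 bpm reads 501 × (50/60)^(1/6) = 486 ms by Bazett, so a Fridericia exceedance is missed.

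**2. Calendar.** Day 1 of Cycles 2, 3 and 4 is study day 29, 57 and 85. The last cobimetinib doses before them are on days 21, 49 and 77. Each gap is 8 days (29 − 21, and so on), with 7 drug-free days between. The visit window of ±3 days makes this 5 to 11 days if the last dose stays on Day 21. The documents do not say whether the Day 1 ECG comes before or after that day's dose. The DLT window is the first 28 days, and its scheduled on-treatment ECG, Cycle 1 Day 15, falls while both oral drugs are being taken.

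**3. What remains on board at the Day 1 ECG.** The documents give no cobimetinib half-life. For assumed values of 24, 48, 72 and 96 h, the fraction left after 8 days (192 h) is 0.5^(192/half-life) = 0.4%, 6%, 16% and 25%. These are drug levels, not QT effects. Hydroxychloroquine has no off-week. Section 10.1.1 gives a blood "half life of 537 hours (22.4 days") and a plasma value of 2,963 hours (123.5 days), so 98.5% to 99.7% remains 12 h after a dose.

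**4. Hydroxychloroquine accumulation.** The fraction of steady state on study day d is 1 − 2^(−(d−1)/half-life in days).

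| Study day | 22.4 days | 123.5 days |
|---|---|---|
| 15 | 35% | 8% |
| 29 | 58% | 15% |
| 57 | 82% | 27% |
| 85 | 93% | 38% |

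**5. The two discontinuation texts.** For a third QTc above 500 ms with a change of 60 ms or less, Section 8.3.1 ends cobimetinib permanently. For the third occurrence under the same condition, Table A1.12 interrupts treatment and lowers cobimetinib and hydroxychloroquine by one further level. Both cannot apply.

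**The case against.** Bazett appears nowhere in the protocol. The only correction named is QTcF, and a change from pre-treatment is most naturally read on the baseline scale. The numerical example needs a patient close to the entry limit. A DLT must also be drug-related with no clear alternative cause, the Principal Investigator is consulted on the final call, and ECGs follow five minutes supine. All of this stands and limits how often the ambiguity would matter. It does not supply the missing definition for a threshold that counts as a DLT and may be applied at affiliate sites.

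On the calendar, Table 10 and its footnote agree with each other, and an ECG at the start of a cycle, when cobimetinib restarts, is a coherent choice. Section 3.3.3 attaches the QT warning to hydroxychloroquine, which Day 1 ECGs do capture. That also stands.

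A reader might infer more than the documents support:
- **That ECG timing makes rules fire falsely or distorts the DLT count.** It does neither. Only the unnamed formula could produce a false reading, and Cycle 1 Day 15 is on drug.
- **That the MTD estimate is biased by false DLTs.** No frequency can be given, because neither the sites' formula nor the distribution of entry QTcF and heart rate is known.
- **That later-cycle QT toxicity in general goes undetected, or that full hydroxychloroquine exposure is reached unmonitored.** Timing can hide only cobimetinib's contribution and any joint effect, and accumulation depends on which stated half-life is used.

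**Conclusion.** The concern holds in two limited parts, both worth correcting. First, the QTc rules leave the correction open while entry fixes it. If Bazett is read, an unchanged patient can meet the 501 ms limit from about 89 bpm at the women's entry limit and about 116 bpm at the men's. The 60 ms limit needs about 124 to 134 bpm, so false permanent stopping under that rule is much less likely. Second, after Cycle 1 the QTc rules that act on cobimetinib rest on scheduled ECGs nominally 8 days after its last dose. How much effect this could hide cannot be quantified: the cobimetinib half-life and the ECG time relative to the Day 1 dose are not given. At Cycle 1 Day 15, the one scheduled ECG that falls within continuous cobimetinib dosing, hydroxychloroquine is at only 8% to 35% of steady state. The contradiction over a third occurrence needs no assumption.

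**What to change.** - State one QT correction, the same as at entry, in Section 4.1.1.1, Section 8.3.1 and Table A1.12, and require it for the pre-treatment value used in the change rules. This is a wording change. It will alter who meets a rule at any site that would have used another formula, which is its purpose.
- Reconcile the ECG calendar (Table 10, footnote 6) with the 21/7 cobimetinib schedule (Table 4) and Table A1.12, so that the post-Cycle-1 cobimetinib QTc rules are informed by ECGs taken during cobimetinib dosing. A Day 15 visit already exists in every cycle, so no visit is added. If an ECG is moved rather than added, none precedes the cobimetinib restart in that cycle; if one is added, the cost is an extra ECG. The calendar should also say whether a Day 1 ECG is taken before or after the dose.
- Reconcile Section 8.3.1 with Table A1.12 for a third QTc above 500 ms with a change of 60 ms or less.

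Thresholds and dose actions are for the sponsor to decide.
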